It is anticipated that about 100 volunteers will be screened in order to enroll a total of 40 participants. The 40 enrolled participants will be evenly split, with 20 in each of the two dosage groups for cAd3-Marburg. The dose escalation plan includes daily review of any new safety data by a study clinician, regular review of safety data by the protocol team and a staged enrollment plan with required interim safety reviews. The study will begin with enrollment of 3 participants into Group 1 at a rate of 1 participant per day. After at least 7 days of follow-up for the first 3 vaccinated participants, an interim safety review will occur before enrollment of additional participants into the group. If no safety issues are identified, an additional 17 participants will be enrolled to complete Group 1. When there is a minimum of seven days of follow-up safety data from the last enrolled participant in Group 1, an interim safety review will occur. Once no safety issues are identified, enrollment of participants into the next dose level will begin with the enrollment of 3 participants at a rate of 1 participant per day. After at least 7 days of follow-up for the first 3 vaccinated participants in Group 2, an interim safety review will occur before the enrollment of additional participants into Group 2. If no safety issues are identified, an additional 17 participants will be enrolled to complete Group 2.

Product Description

VRC-MARADC087-00-VP is formulated at 1×10^{11} PU/mL.

VRC-DILADC065-00-VP diluent is the formulation buffer used for vaccine production and will be used when needed to prepare the 1×10^{10} PU/mL dose of cAd3-Marburg.

Participants

Healthy adult volunteers, 18 to 50 years old will be enrolled.

Study Duration

Participants will be evaluated by 9 clinic visits over 48 weeks.

Study Objectives**Primary Objectives**

- To evaluate the safety and tolerability of VRC-MARADC087-00-VP when administered IM at a dose of 1×10^{10} particle units (PU) to healthy adults;
- To evaluate the safety and tolerability of VRC-MARADC087-00-VP when administered IM at a dose of 1×10^{11} PU to healthy adults.

Secondary Objectives

- To evaluate the antibody response to the GP insert and cAd3 vector in VRC-MARADC087-00-VP at 4 weeks after vaccination as assessed by GP ELISA and vector-specific neutralization assays, respectively.

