Published data in support of evaluating cAd3 vectors for a next generation Marburg vaccine comes from the Phase I, dose-escalation, open-label trial of cAd3-EBO performed by Ledgerwood, *et al.* [16]. Twenty healthy adults, sequentially enrolled in two groups of 10, received IM doses of 2×10^{10} particle units or 2×10^{11} particle units. No safety concerns were identified although, transient fever developed within 1 day after vaccination in two participants in the high dose group. Glycoprotein-specific antibodies were induced in all 20 participants, however the high dose group developed antibodies of higher magnitude and more frequent CD4 and CD8 T cell responses to vaccine antigen. Other studies evaluating this product in U.S., Swiss

and Malian adults showed the Ebola cAd3 vaccine to be safe and immunogenic [16-19]. Similar cAd3 Marburg GP doses will be tested in this slowly enrolling, staged, dose-escalation study.

In summary, use of the recombinant, non-replicating cAd3 vector for construction of the cAd3-Marburg vaccine is based on its properties to induce immune responses as readily as rAd5, but with little to no pre-existing immunity in human populations. The encoded WT GP antigens were chosen based on preclinical data and may provide protective immunity against Marburgvirus species and on their demonstrated safety in humans when expressed by a DNA plasmid.

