8.2. Sample Size and Accrual

8.2.1. Power and Sample Size Calculations for Safety

The goal of the safety evaluation for this study is to identify safety concerns associated with vaccination. Occurrence of solicited local and systemic reactogenicity symptoms, occurrence of adverse and serious adverse events will be assessed as the proportion of participants experiencing such safety event. Table 4 below shows 95% confidence intervals for 0, 1, 2, 5, and 10 participants with observed events in each group or among all study participants.

Table 4: Exact 95% Confidence Intervals for the Proportion of Participants Experiencing a Safety Event

| Group | Sample Size | Number of Participants with an Event(s) Observed | | | | |
|-----------------------------|-------------|--|-----------------------|---------------------|-----------------------|----------------------|
| | | 0 | 1 | 2 | 5 | 10 |
| Each Individual Study Group | 20 | 0% (0%-16.8%) | 5% (0.1%-24.9%) | 10% (1.2%-31.7%) | 25% (8.6%-49.1%) | 50% (27.2%-72.8%) |
| All participants | 40 | 0% (0%-8.8%) | 2.5% (0.06%-13.2%) | 5% (0.6%-16.9%) | 12.5% (4.2%-26.8%) | 25% (12.7%-41.2%) |

If no participants experience an event, the upper limit of a two-sided exact 95% CI would be 16.8% for an individual group and 8.8% for the entire study group. While this study is not necessarily powered to detect differences between groups, we would have 82% power to detect a difference of 40% ($p_1=0.1$ and $p_2=0.5$) using Barnard's exact unconditional test at a 5% two-sided level of significance.

Changes in laboratory measures from baseline will also be described. For continuous safety measures, Table 5 below shows minimum detectable changes from baseline to a specified time point using a paired t-test with a two-sided 5% level test.

Table 5: Minimum Detectable Differences, in Standard Deviations, for Change From Baseline to a Single Time (2-sided $\alpha=0.05$)

| Group | Sample Sizes | Power | | |
|-----------------------------|--------------|-------|------|------|
| | | 80% | 85% | 90% |
| Each Individual Study Group | 20 | 0.66 | 0.71 | 0.76 |
| All participants | 40 | 0.45 | 0.49 | 0.53 |

If comparing the two study groups, we would have 80% power to detect a difference of 0.91 standard deviations using a two-sample t-test at a two-sided 5% alpha and assuming equal variances.

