8.3.3. Immunogenicity Analysis

Immunogenicity analysis will consist of all vaccinated participants. If assay data are qualitative (i.e., positive or negative) then analyses will be performed by tabulating the frequency of positive response for each assay at each timepoint that an assessment is performed. Binomial response rates will be presented with their corresponding exact 95% confidence interval estimates. Barnard's exact unconditional tests will be used to compare the two groups to each other. For quantitative results, mean and standard deviation will be calculated. One-sample t-tests will be used to assess the changes from baseline. Two-sample t-tests will be used to compare the two study groups. Missing responses will be assumed to be missing at random, i.e., conditional on the observed data the missingness is independent of the unobserved responses. Graphical descriptions of the longitudinal immune responses will also be given.

Some immunologic assays have underlying continuous or count-type readout that is often dichotomized into responder/non-responder categories. For these assays, graphical and tabular summaries of the underlying distributions will be made. These summaries may be performed on transformed data (e.g., log transformation) to better satisfy assumptions of symmetry and homoscedasticity.

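### The two doses are compared by significance tests only; add an estimated between-dose difference with a 95% interval wherever they are compared.

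*Combined protocol and SAP*

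**What the plan says.** The allocation is fixed in the Schema: "The 40 enrolled participants will be evenly split, with 20 in each of the two dosage groups for cAd3-Marburg". Group 2 opens only after Group 1 is full and its safety data have been reviewed (Schema and section 4.0).

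For immunogenicity, section 8.3.3 plans the following:
- Binary assays within a group: "Binomial response rates will be presented with their corresponding exact 95% confidence interval estimates".
- Binary assays between groups: "Barnard's exact unconditional tests will be used to compare the two groups to each other".
- Quantitative assays within a group: "For quantitative results, mean and standard deviation will be calculated", with one-sample t-tests for change from baseline.
- Quantitative assays between groups: "Two-sample t-tests will be used to compare the two study groups".

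For safety, section 8.3.2 gives exact intervals for reactogenicity. If the groups are compared at all, it names Barnard's test for binary variables and t-tests or Wilcoxon rank sum tests for continuous ones.

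Section 8.2.1 opens its between-group power statement with "While this study is not necessarily powered to detect differences between groups", then gives 82% power for 10% versus 50% and 80% power for 0.91 SD. Section 8.2.2 applies the safety precision and power calculations to immunogenicity.

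Nothing in sections 8.2 or 8.3 specifies a risk difference, a mean difference or a ratio of geometric means with an interval, or says how a non-significant comparison should be read.

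**The concern.** A p-value from a comparison with limited power says little. When it exceeds 0.05, the reader needs to know which differences the data still allow, and only an estimate with an interval shows that. The plan supplies intervals for each group separately and stops short of the difference, which is the quantity that the between-group tests address.

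At stake is how the immunogenicity results of the two doses can be interpreted side by side. Section 8.3.4 says that immunogenicity analyses may inform later decisions about the vaccine. If an interval is added only after the data are seen, its method and scale (raw or log) are chosen then too. Section 8.3.3 says only that some summaries may use transformed data.

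**Working it through.** **Inputs from the documents.** 20 per group (Schema); two-sided 5% level, 82% power for 0.1 versus 0.5 by Barnard's test, 80% power for 0.91 SD by two-sample t-test (section 8.2.1). All 20 per group are taken as evaluable, since no dropout rate is given.

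**1. The plan's own figures.** Barnard's test was enumerated over all 21 × 21 possible tables, with the p-value maximised over the common rate. Power at 0.1 versus 0.5 is 82.2% (stated: 82%). The noncentral t with 38 degrees of freedom gives a detectable difference of 0.909 SD at 80% power (stated: 0.91). Both figures reproduce, so the method below matches the plan's.

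**2. Proportions: what a non-significant result leaves open.** Intervals are 95% Miettinen-Nurminen score intervals for the difference.

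| Observed | Difference | Barnard p | 95% interval (points) |
|---|---|---|---|
| 2/20 vs 6/20 | 20 points | 0.15 | -6 to +44 |
| 4/20 vs 9/20 | 25 points | 0.11 | -4 to +51 |
| 10/20 vs 16/20 | 30 points | 0.053 | about 0 to +55 |

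None of the three is significant, and each is compatible with a difference of more than 40 points. In the last row the score interval's lower limit sits at about zero while Barnard's p is just above 0.05. Interval and test can therefore disagree at the margin, which is a reason to fix the interval method in advance.

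**3. Means.** Half-width of the 95% interval = t(0.975, 38) × √(1/20 + 1/20) = 2.024 × 0.316 = 0.64 SD.
- Observed difference 0: -0.64 to +0.64 SD.
- Observed 0.3 SD (p = 0.35): -0.34 to +0.94 SD.
- Observed 0.6 SD (p = 0.065): -0.04 to +1.24 SD.

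A t-test just short of significance has an upper limit near 2 × 0.64 = 1.28 SD. The documents give no assay SD. Assuming a log10 titre SD of 0.3 to 0.6, that limit is a ratio of 10^(1.28 × 0.3) = 2.4 to 10^(1.28 × 0.6) = 5.9.

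**4. GP ELISA response rates if both doses are near the ceiling (an assumption).** When the high dose gives 20/20, Barnard's test rejects only if the low dose gives 16/20 or fewer (16/20: p = 0.039; 17/20: p = 0.086). With a true high-dose rate of 100%, power is therefore P(X ≤ 16) for X binomial with n = 20:
- true low-dose rate 90%: 13.3%;
- true low-dose rate 95%: 1.6%;
- 80% power needs a low-dose rate of about 74%.

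Away from the ceiling the test is more useful. For an illustrative 32% versus 70%, power is 66%.

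**The case against.** The strongest reply is that estimation is already the plan's main approach. Exact intervals are specified for every response rate and for reactogenicity, means and SDs are given by group, and Table 4 is a precision table. A reader could work out a difference and an interval from that output, and naming a test does not mean that the p-value will be reported alone. This is largely fair, and it limits the severity. It does not supply a prespecified estimate, method or scale.

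Four stronger readings are tempting, and the documents do not support them.
- **That the plan will treat non-significance as no dose effect.** No section says so, and section 8.2.1 cautions about between-group power and states the detectable differences.
- **That dose comparison is the trial's main product or feeds a dose-selection rule.** Sections 2.1 and 2.2 list safety at each dose and Week 4 responses. No comparative objective or selection rule appears, and safety comparisons are conditional.
- **That the GP ELISA rate comparison is bound to be empty.** Section 1.2.2 reports of a related cAd3 Ebola vaccine that "Glycoprotein-specific antibodies were induced in all 20 participants", but that product has different inserts and was given at twice these particle doses. The same account notes higher antibody magnitude and more frequent T-cell responses at the high dose. Section 1.2.1 reports a 32% antibody response to a Marburg GP DNA vaccine, which is a different platform. The ceiling is possible but not established.
- **That large differences stay open in both directions.** In the rate examples the interval excludes a large difference favouring one side. Two-sided ambiguity needs nearly equal observed results.

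A limit on the remedy also stands. The groups are enrolled sequentially and without randomisation, so an interval for the difference does not cover differences between the two sets of participants or enrolment periods.

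**Conclusion.** The point holds as a gap in what is prespecified. Between-dose comparisons are defined by tests alone, and at 20 per group a non-significant test can coexist with differences of more than 40 points in a rate or around 1 SD in a mean. The calculations assume complete data in both groups and, for means, a common variance. The fold-change range rests on an assumed assay SD, and the ELISA ceiling case on an assumed similarity to the Ebola vaccine.

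Severity is low. The primary safety description by dose is unaffected, immunogenicity is secondary, and no design feature or planned decision changes. The amendment is still worth making before analysis, because it improves what can be concluded from comparisons that section 8.3.3 commits to making.

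**What to change.** In sections 8.3.2 and 8.3.3, wherever the doses are compared:
- Report the difference in proportions with a 95% interval, naming one method in advance: Miettinen-Nurminen score or exact unconditional.
- Report the Week 4 difference in mean response with its 95% interval. Where data are log-transformed, give it as a ratio of geometric means.
- Present the Barnard, t-test and Wilcoxon p-values as secondary.
- State that non-significance is not evidence of equal response, and that the interval reflects sampling error only because enrolment is sequential and non-randomised.
- State that if GP ELISA response rates prove near 100% at both doses, the rates are descriptive and the Week 4 magnitude comparison, already planned, carries the dose information.

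The cost is SAP wording and one extra column per comparison table. No participants, samples or visits are added, and the sample size stays as it is.

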8.3.4. Interim analyses

Safety Reviews: The PSRT will review safety data routinely throughout the study. The study will utilize both electronic database features and reviews by designated safety review personnel to identify in a timely manner if any of the safety pause rules of the study are met.

Immunogenicity Review: Periodic analyses of immunogenicity for each group may be performed during the study for the purpose of informing future vaccine-related decisions in a timely manner once there are at least 3 participants in the group with the 4 weeks post vaccination follow-up completed. The results will not influence the conduct of the trial in terms of early termination or later safety or immunogenicity endpoint assessments.

9.0 SAMPLE AND DATA MANAGEMENT

9.1. Plan for Use and Storage of Biological Samples

9.1.1. Use of Samples, Specimens and Data

Samples, specimens and data collected under this protocol may be used to conduct protocol-related safety and immune response evaluations, exploratory laboratory evaluations related to the type of infection the study agent was designed to prevent, exploratory laboratory evaluations related to vaccine or infectious disease research in general and for research assay validation. Genetic testing will be performed in accordance with the information included in the study informed consent for genetic testing (Appendix 2C). Results from genetic testing will not be provided to participants as the test results are not validated for clinical use. Safety labs may be completed by Quest Diagnostics Inc.

Immunogenicity of the VRC-MARADC087-00-VP vaccine will be evaluated as humoral and cellular immune responses assessed by ELISA and intracellular cytokine staining (ICS) assay. Other measures of immunogenicity may be also conducted as exploratory evaluations. The ELISA assay will be performed at the VRC or VIP and the exploratory evaluation of Marburg-specific neutralizing antibodies will be conducted at the VRC, using previously published methods [12]. The pre-existing and post-vaccination presence of cAd3 neutralizing antibody also will be evaluated [27]. The ICS assay quantitates the frequency of CD4⁺ and CD8⁺ cells that produce interleukin-2, interferon-gamma and/or tumor necrosis factor in response to pools of overlapping peptides representing Marburg GP antigens and is based upon previously published methods [30].

Other measures of immunogenicity may be conducted as exploratory evaluations. Specific peptides may be used to detect T-cell responsiveness by an enzyme-linked immunospot (ELISpot) assay, modified from a previously published method [31]. Genetic factors associated with immune responses may also be evaluated; isolation of MAbs to determine epitope specificity and function capacity may be performed; and time courses of immune responses may be analyzed including durability of cAd3 neutralizing antibody titers, mediators of inflammation following vaccination, and, for the first week, vaccine-induced mRNA expression profiles and plasmablasts to follow lineage development of anti-GP antibodies.

Stored samples from vaccine study participants may also be used in the future for evaluation of immune response to the vaccine as measured by other assays. The experimental laboratory procedures for the exploratory objectives may be conducted using fresh or stored samples at the NIH or at the laboratories of its affiliates and/or collaborators (see Appendix 16).

9.1.2. Storage and Tracking of Blood Samples and Other Specimens

All of the stored study research samples will be labeled with a participant ID number that only the site can link to the participant. Samples will be stored at VIP, Gaithersburg, MD or at VRC Immunology Laboratory in Building 40; all are secure facilities with limited access. Data will be kept in password-protected computers. Only investigators or their designees will have access to the samples and data. Samples will be tracked in the Laboratory Information Management System (LIMS) database or using another software designed for this purpose (e.g., Freezerworks).

9.1.3. Disposition of Samples, Specimens and Data at Completion of the Protocol

At the time of protocol termination, samples will remain at VIP, VRC or, after IRB approval, transferred to another repository. At this time, a list of all participants who refused future use of their samples will be generated from the study database and the corresponding samples will be destroyed. Data will be archived by the VRC in compliance with requirements for retention of research records, or after the IRB and the IND sponsor approval, may be either destroyed or transferred to another repository.

9.1.4. Loss or Destruction of Samples, Specimens or Data

Any loss or unanticipated destruction of samples (for example, due to freezer malfunction) or data (for example, misplacing a printout of data with identifiers) that compromises participant confidentiality or the scientific integrity of the study will be reported to the IRB in accordance with institutional policies. The PI will also notify the IRB if the decision is made to destroy the remaining samples.

9.2. **Study Documentation and Storage**

The investigator will maintain a list of appropriately qualified persons to whom trial duties have been delegated.

Source documents are original documents, data, and records from which the participant's data are obtained. These include but are not limited to hospital records, clinical and office charts, laboratory and pharmacy records, diaries, microfiches, radiographs, and correspondence.

The investigator and staff are responsible for ensuring maintenance of a comprehensive and centralized filing system of all study-related (essential) documentation, suitable for inspection at any time by representatives of USAMRMC ORP HRPO, WRAIR IRB, FDA, the U.S. DoD, the sponsor, and other regulatory agencies. Essential documents for all study participants are to be maintained by the investigators in a secure storage facility. Elements include:

- Participant files containing completed informed consent forms, and copies of source documentation (if kept)
- Study files containing the protocol will include all amendments and copies of correspondence between the study site, protocol team and the IRB
- All Essential Documents outlined in the ICH Good Clinical Practice Guideline.

In addition, all original source documentation must be maintained and be readily available for monitoring or auditing purposes.

All essential documentation will be collected by EMMES in the Regulatory Tracking System and should be retained for the same period of time required for medical record retention. The FDA requires study records to be retained for 2 years after marketing approval or refusal (21 CFR 312.62) and the NIH requires study record retention for a minimum of 7 years after study closure. Study records will be retained for at least as long as is required by the FDA and NIH record retention requirements. No study document or data should be destroyed without prior written agreement between VRC, the MHRP Consultants and the PI. Should the PI wish to assign the study records to another party or move them to another location, VRC must be notified in writing of the new responsible person and/or new location.

The VRC may request to receive a copy of all essential documents. FDA form 1572, CVs and IRB approvals must be submitted to the VRC as IND Sponsor.

9.3. Data Collection

Clinical research data will be collected in a secure electronic data management system through a contract organization, EMMES (Rockville, MD). Data entered into the electronic data system shall be performed by authorized individuals. Corrections to the electronic data system shall be tracked electronically (password protected) with time, date, individual making the correction, and what was changed.

The investigator is responsible for assuring that the data collected is complete, accurate, and recorded in a timely manner. Source documentation (the point of initial recording of information) should support the data collected in the system, and must be signed and dated by the person recording and/or reviewing the data. Extracted data without participant identifiers will be sent to the Protocol Statistician for statistical analysis.

This data will not contain participant names or Social Security or other identification number, but is referenced only by the study specific identification code.

Every attempt must be made to adhere to the approved protocol and to obtain and record all data requested for each participant at the specified times. However, ethical considerations or other events may result in the failure to obtain and record certain data, or to record data at the times specified. If this occurs, the events and, the reasons for the event must be clearly documented on the CRF for deviations and reported as described applicable.

Analysis files are created on a periodic basis and made available to the MHRP Consultants, Principal Investigator (PI), and Associate Investigators (AIs). Other collaborators may be given access to these analysis files, or data gathered from them, at the direction of the PI.

